#### **The clinical trial will:**

- a. Assess aggregate time spent in seven primary clinical states of BD (remitted; subsyndromal depression, mania or mixed state; and syndromal depression, mania or mixed state).
- b. Assess the weekly completion of KIOS-Bipolar and eMoods.
- c. Determine indices of patient satisfaction with the format, ease of use, time required and patient motivation for continuing use of the patient tools both during the trial and following completion.
- d. Determine patient satisfaction with the clinical information on BD illness trajectory and recommendations to facilitate good health and effective interventions. Note that eMoods does not provide this element of information, therefore no comparative data will be feasible for this one objective.
- e. Assess patient scored life function indices (Life Function Questionnaire (LFQ) over the 52 week period of the study.
- f. Assess the relationship between the 8 symptom items in K-B with relevant items rated both by clinicians and as self-assessments by patients at seven time points (week 0, 8, 16, 24, 32, 40 and 52) in the study. These are times at which clinical care visits will routinely occur, and therefore will not add either to extra burden on the participants, or extra contact time with staff. Subjects randomized to eMoods will be similarly scheduled, with the correlations limited to those feasible with the eMoods product. Self-assessments with the 27 item BISS-Self are routinely obtained as part of regular treatment visits.

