**Early termination:**

Participation in the study will be terminated if a patient has a score of 4 on the BISS suicide item, BISS-Depression Scale  $\geq 50$ , or BISS Mania Scale  $\geq 35$  for 4 consecutive weeks, or if the treating psychiatrist determines that a patient poses an imminent risk of self-harm.

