#### **ASSESS KIOS-BIPOLAR OR eMOODS:**

- a. At the beginning of the study subjects will be provided preformatted evaluation sheets and will be encouraged to note observations regarding ease/benefits of use, impediments to use, and suggestions for additional features that would enhance the utility of KIOS-Bipolar or eMoods for sustained health.
- b. We will ask the subjects to estimate how completing the KIOS-Bipolar /eMoods assessments contributed to their self-awareness, attitude, and overall sense of satisfaction with their health status.
- c. We will assess the sensitivity of KIOS-Bipolar to identify improving or worsening by comparing the concordance between subject-assessed items with staff -administered BISS items that address similar symptoms.

**Plan of analysis:** The primary aims of the analyses are to investigate patterns of adherence and attrition. The term adherence refers to the extent to which participants follow the weekly completion of KIOS-Bipolar's eight pivotal symptoms of bipolar disorder. Adherence will be measured through such usage indicators as the proportion of weeks completed on time, the proportion completed only with follow-up prompts, and the number of weeks not submitted. Proportions of stable trajectories or improving trajectories are of primary interest. With  $n=90$  subjects (which allows for as many as 30 of the enrolled 120 subjects to have met some criterion for early termination) in the study we will be able to estimate any proportion within 0.10 with 95% confidence. For proportions larger than 0.9 we will be 95% confident we are within 0.06 of the true proportion. For a trajectory neither improving nor degrading there should be a 0.5 proportion

UTHSCSA tracking number: HSC20150321H

of each. For any hypothesis test for a proportion improving or degrading, i.e. not 0.5, we have 0.80 power at two tail significance of 0.05 to detect 0.65 different from 0.5 with n=90 subjects. For subgroups of patients with n=45 we can detect 0.71 different from 0.5 and with n=30 we can detect 0.74 different from 0.5. When comparing proportions of two subgroups of subjects, we will be 95% confident that the difference in proportions of the two subgroups is less than 0.25 for subgroups of n=30 and smaller than 0.20 for subgroups of size 40. If the proportions are larger than 0.9 (i.e. less variable), then we will be 95% confident that the difference in proportions of two subgroups with n=30(45) is less than 0.15 (0.12).

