Assumptions needed for each analysis will be examined to assure they are reasonably well met and the conclusions are valid. End of study overall improvement or not for each measure can be analyzed with logistic regression using covariates and predictors of interest. By focusing analyses on proportions and changes in trajectories, each subject will serve as their own control and trends in improved scores, symptoms and behavior may be identified.

Initially, we will also assess the effects of site, ethnicity, and bipolar disorder subtype (BD I, BD II), but none of these factors will be retained in the final model if they are not shown to be significant moderating factors.

The rate of dropout at any given time will be modeled through logistic regression models, with health, socioeconomic, and treatment factors as explanatory variables. *The impact of quality of life on dropout will be assessed similarly.*

**Outcome Measures from KIOS Analytics:** Knowledge Base performance metrics will be computed to measure the effectiveness of the content provided to patients. These metrics take several forms and are based on changes in the symptom scores for all subjects in the field trial (see Phase I Final Report). Changes in the symptom scores provide a global measure of efficacy. Each of these measures can be computed as a function of changes, either over the course of the entire field trial or at each incremental assessment. This latter approach will provide a measure of effectiveness over time. Other KIOS analytic methods will reveal which specific content in the knowledge base needs improvement. Behavioral frequency analysis will show which patient states are entered most frequently. Behavioral transition analysis will show which conditions are precedents to undesirable states.

**Implementation of Clinical Trial Results into Final Product:** The results of the randomized trial will be used to make further refinements to KIOS-Bipolar. The KIOS-generated results will be used to guide changes to the knowledge base. Suggestions about additional features will be considered in development of the commercialization plans.

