### ***e. Protections Against Risk***

Minimal risk to subjects or subject's privacy is anticipated. Nonetheless, we recognize the need for strict protection of confidentiality in this study. To address this, records of patients will be retained as required by statute in locked files. All computer files will be password protected. Subjects will be identified in common-use computer files by ID number only. Research reports and publications will report only group data and not individual names. Identities of subjects will not be revealed in the publication or presentation of any results from this project. All investigators and research staff at the respective institutions have completed the requirements for human research subjects' protection. All investigators and research staff at BDC have completed the requirements for human subjects' protection. The study will be performed in accordance with HIPPA regulations and approved by the IRBs at the UTHSCSA, the University of Louisville and the University of Cincinnati.

Participation in the study will be terminated if a patient has a score of 4 on the BISS suicide item, BISS Depression Scale  $\geq 50$ , or BISS Mania Scale  $\geq 35$ , or if the treating psychiatrist determines that a patient poses an imminent risk of self-harm.

All subjects enrolled in the trial will have been under care of a psychiatrist at their respective institutions prior to enrolling in the study. All subjects will continue to receive evidence-based care provided by outstanding psychiatrists at the three sites. Participation in the study will not impact the patient's routine clinical care for his/her bipolar condition. The study's planned visits will generally be scheduled to coincide with the patient's regularly scheduled clinic visits both for convenience and in order to not interfere with regular care.

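### The early-termination rule is stated two ways and terminated subjects get no outcome, so tests of improvement run only on those who remain could be biased toward improvement

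*Combined protocol and SAP*

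**What the plan says.** **Sizing and test.** The Plan of analysis (under Assess KIOS-Bipolar or eMoods) calls proportions with stable or improving trajectories of primary interest. The null is that "For a trajectory neither improving nor degrading there should be a 0.5 proportion" of each. The power statement reads "For any hypothesis test for a proportion improving or degrading, i.e. not 0.5, we have 0.80 power at two tail significance of 0.05", for 0.65 with n=90. The figure of 90 is explained as one "which allows for as many as 30 of the enrolled 120 subjects to have met some criterion for early termination". The plan adds that "each subject will serve as their own control", and that "End of study overall improvement or not for each measure can be analyzed with logistic regression using covariates and predictors of interest".

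**Termination rule.** The Early termination section lists a top score on the BISS suicide item, a BISS depression score of at least 50, or a BISS mania score of at least 35, then continues "for 4 consecutive weeks, or if the treating psychiatrist determines that a patient poses an imminent risk of self-harm". Protections Against Risk opens the same list, "Participation in the study will be terminated if a patient has a score of 4 on the BISS suicide item, BISS Depression Scale", and carries it through with the same cut-offs but no duration.

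**Rating schedule.** Objective f and Table 1 place the clinician BISS "at seven time points (week 0, 8, 16, 24, 32, 40 and 52) in the study".

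**Missing outcomes.** Dropout is to be modelled by logistic regression as an outcome in its own right. No section states the analysis set for the improvement tests, or whether a terminated subject is left out, scored on the last observation, or counted as not improved.

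**The concern.** Subjects leave largely because of high scores on the kind of symptoms that the improvement analysis measures. The tests against 0.5 have no comparator, so nothing offsets a selective loss of people who are doing badly. An analyst who tests the 90 who remain and one who tests all 120 on their last observation would both be following the text, and could reach different conclusions. The dropout model describes attrition but gives nobody an improvement outcome.

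The membership of the excluded group is unsettled too. One statement of the rule requires persistence and the other does not, so the number and kind of subjects removed depend on which page a site follows. Whether the duration applies to all three BISS criteria or only to the last is also not clear from the sentence.

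**Working it through.** **1. The plan's own figure.** Exact two-sided binomial test against 0.5 at 0.05, n=90: reject upward at 55 or more. Power at 0.65 is 0.812 (continuity-corrected normal 0.793), against a stated 0.80. Also 90/(1 − 30/120) = 120. The sizing reproduces.

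**2. Termination rule against the schedule.** Gaps between BISS visits at weeks 0, 8, 16, 24, 32, 40 and 52 are 8, 8, 8, 8, 8 and 12 weeks. No two scheduled ratings fall within four weeks of each other.

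**3. When remaining-only is biased.** Let p be the proportion of all 120 who improve by end of study, R the number terminated, and W those of the R who would be non-improvers. The expected proportion among those who remain is

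(120p − (R − W)) / (120 − R),

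which exceeds p exactly when W/R > 1 − p. The threshold is one half at p=0.50 and 35% at p=0.65.

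**4. Size under a true 0.50.** R and W are assumptions; the documents give only the ceiling R=30. Two removal models are used. In the fixed-count model X ~ Bin(120, 0.5) and R − W improvers are removed. In the independent model those remaining are Bin(120 − R, (60 − (R − W))/(120 − R)). Upper critical counts are 66/110, 61/100 and 55/90. The nominal upper-tail error is 0.025.

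| R | W | Expected proportion among remaining | False improvement, fixed-count / independent |
|---|---|---|---|
| 10 | 5 | 55/110 = 0.500 | 0.027 / 0.022 |
| 10 | 10 | 60/110 = 0.545 | 0.158 / 0.146 |
| 20 | 15 | 55/100 = 0.550 | 0.158 / 0.134 |
| 30 | 15 | 45/90 = 0.500 | 0.041 / 0.022 |
| 30 | 22 | 52/90 = 0.578 | 0.324 / 0.298 |
| 30 | 23 | 53/90 = 0.589 | 0.392 / 0.376 |
| 30 | 30 | 60/90 = 0.667 | 0.842 / 0.890 |

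At W = R/2 there is no bias. The excess over 0.025 in the fixed-count column reflects its larger variance, not a shift.

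**5. Transient or persistent severity.** W refers to status at end of study, not at the trigger, and the two can differ widely. This was simulated under assumptions not in the documents: severity stationary over 52 weeks, first-order autoregressive with weekly correlation 0.5 to 0.95, 25% terminated at a high score on a scheduled visit, true week-52 improvement 0.50.

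- Of those terminated, 90-97% were worse than baseline at the trigger, but only 47-50% at week 52.
- Remaining subjects only: 0.49-0.50 improving, no upward bias.
- All 120 on last observed status: about 0.38-0.43 improving across runs. At 0.38-0.39, a false degrading result occurred in 0.60-0.70 of trials.

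When severity instead followed a random walk, so that worsening persisted, the order reversed: remaining-only was biased upward (0.64 in one setting) and last observed status was close to the truth (0.48). The size depends on the assumed step.

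**6. Termination counted as not improved.** Under a true 0.50 with R=30, the expected proportion is (60 − (30 − W))/120: 0.375 at W=15, and 0.433-0.442 at W=22-23. False results below 0.5 follow in about 74% and 21-26% of trials. This scoring is not neutral either.

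**The case against.** The strongest case against has four parts.

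- **The plan never says that the tests are restricted to the 90.** That is right: 90 is a sizing figure and 30 an upper allowance. A reader might infer that the analysis will drop terminated subjects. The documents do not support this; they simply leave it open.
- **Termination is not worsening.** The BISS criteria are severity levels, not changes, and eligibility sets no ceiling on baseline severity. The disease is described as recurrent, so a subject severe at the trigger may have recovered by week 52. This stands, and it is why the bias is conditional.
- **Large scenarios rest on the ceiling.** If the four-week condition governs, few score-based terminations could be confirmed at scheduled visits, and far fewer than 30 might occur. With 10 terminated the shift is modest even when all are non-improvers (0.545).
- **Reach.** The listed hypotheses compare arms, and the plan names adherence and attrition as its primary aims. A reader might infer that the KIOS-Bipolar v eMoods comparison is biased as well; that would require termination to differ between arms, which nothing in the documents indicates. The one-sample tests still matter, because the plan calls improving trajectories of primary interest.

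A reader might also infer that keeping all 120 on last observed status removes the problem. It does not: an error rate at or below nominal under that rule assumes that last observed status is the true outcome, and step 5 shows that it can mislead in the opposite direction.

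**Conclusion.** Two defects are established from the text alone. The termination rule is stated inconsistently and cannot be verified from the BISS schedule in its four-week form. And subjects who meet it have no assigned outcome in the improvement tests.

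The bias is a possibility, not a demonstrated fact. It needs a remaining-only analysis and terminated subjects who would be disproportionately non-improvers at end of study. Its size runs from nil, at half non-improvers or with transient episodes, to about 0.15 with 10 terminated and all non-improvers, and 0.30-0.39 with 22-23 of 30. The 0.84-0.89 figure is the extreme corner: the plan's ceiling with every terminated subject a non-improver. No single scoring rule is unbiased across the plausible courses of illness, so none should be presented as such. This should be fixed before analysis; confidence in the size is medium because the key share is unknown.

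**What to change.** 1. **Reconcile the termination rule.** Bring the Early termination section and Protections Against Risk into agreement with each other and with the rating schedule in objective f and Table 1. State which criteria any duration applies to and which assessments establish it. Which rule is right is a clinical matter for the investigators.
2. **Define the outcome and the set.** State what counts as improving, on which instrument and at what time, for all 120 randomised subjects in their assigned arm. The trajectories come from weekly app entries, whereas the trigger is a clinician BISS score or a psychiatrist's judgement, so the last observation must be specified. eMoods users may hold data until a visit, so say how their last entries are retrieved.
3. **Report three scorings side by side:** remaining subjects only, last observed status, and termination counted as not improved. Present none of them as the unbiased answer.
4. **Limit the claim.** Do not claim improvement if it appears only among non-terminated subjects.

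**Cost.** Protocol and analysis-plan wording, a little more analysis, no new visits, and a more cautious claim. Power with all 120 is 0.89 if 0.65 holds throughout. If 0.65 holds only in the 90 who remain and 7-8 of 30 terminated improved, the overall proportion is (58.5 + 7 or 8)/120 = 0.546-0.554 and power is 0.09-0.13. With 10 terminated and none improved it is 71.5/120 = 0.596 and 0.50. That loss reflects a smaller effect in the whole cohort, which the report should show.

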**C. Hypotheses:**

a. Patients randomized to KIOS- Bipolar compared with those randomized to eMoods will have a higher proportion of time in remitted status, lower proportion in syndromal status (Manic, depressed, mixed) and higher

LFQ scores.

- b. Persistence with use of KIOS- Bipolar and eMoods will not differ. Persistence is defined as 1) the proportion of subjects who complete weekly scheduled use of the bipolar self-assessment scales and 2) completion of the 52 week self-assessment protocol.
- c. The proportion of on-time completion of assessments will not differ between groups.
- d. Subject satisfaction, assessed by qualitative questionnaires completed by subjects during and principally shortly following completion or discontinuation of the trial, will not differ between groups.
- e. LFQ subscales will be associated with superior outcomes for the KIOS-Bipolar group.
- f. Correlations between scores on items included in KIOS- Bipolar and similar items on the BISS SR and the BISS 42 will be conducted. Strength of association will be higher between KIOS- Bipolar and BISS comparisons than eMoods-BISS comparisons.
- g. Aggregate changes for the KIOS- Bipolar items and corresponding eMoods items will indicate greater proportions of decreased scores for KIOS- Bipolar

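### Hypotheses a, e and g claim that KIOS-Bipolar does better than eMoods, but the plan names no between-arm analysis for them, and its stated power is for a one-sample test against 0.5

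*Combined protocol and SAP*

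**What the plan says.** Section C (Hypotheses) makes three directional claims about outcome.

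- Hypothesis a: "Patients randomized to KIOS- Bipolar compared with those randomized to eMoods will have a higher proportion of time in remitted status", together with less time in syndromal status and higher LFQ scores.
- Hypothesis e: "LFQ subscales will be associated with superior outcomes for the KIOS-Bipolar group".
- Hypothesis g: "Aggregate changes for the KIOS- Bipolar items and corresponding eMoods items will indicate greater proportions of decreased scores for KIOS- Bipolar".

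The Plan of analysis, under the heading ASSESS KIOS-BIPOLAR OR eMOODS, gives adherence and attrition as its primary aims. It also gives primary interest to the share of trajectories that are stable or improving. Its power statement reads "we have 0.80 power at two tail significance of 0.05 to detect 0.65 different from 0.5 with n=90 subjects". The 90 is the 120 enrolled less up to 30 early terminations. The same kind of statement follows for subgroups of 45 (0.71 against 0.5) and 30 (0.74 against 0.5). A further sentence bounds the difference in proportions between two subgroups, without saying which subgroups.

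On modelling, the plan says "End of study overall improvement or not for each measure can be analyzed with logistic regression using covariates and predictors of interest", and explains that by its focus on proportions and trajectories "each subject will serve as their own control". Treatment is named as an explanatory variable only in the dropout model: "with health, socioeconomic, and treatment factors as explanatory variables". Site, ethnicity and bipolar subtype are examined, but "none of these factors will be retained in the final model if they are not shown to be significant moderating factors".

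**The concern.** The trial is randomized and its title promises a comparison of two tools. Hypotheses a, e and g can be answered only by a contrast between the arms. A test of whether more than half of all subjects improve answers a different question: whether subjects changed over the year. Section e (Protections Against Risk) says that all subjects continue in psychiatric care, so change shared by both arms is plausible.

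As written, the plan could end with a significant result against 0.5 and no pre-specified analysis of whether the arms differ. The choice of outcome, model and handling of app switchers would then be made after the data are seen. A reader looking for the power of the comparison would find only the 0.80, which does not describe it.

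**Working it through.** **Inputs.** From the Plan of analysis: two-sided 0.05, power 0.80, null 0.5, alternative 0.65, n = 90 (120 − 30), and subgroups of 45, 40 and 30. The documents give no allocation ratio, SD, remission rate or target difference. I assume 1:1, so 45 per arm after the allowed loss, or 60 per arm with no loss.

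**1. The plan's own figure.** One-sample test of 0.65 against 0.5, n = 90.
- Normal approximation: z = (0.15 × √90 − 1.96 × √0.25) / √(0.65 × 0.35) = (1.423 − 0.980) / 0.477 = 0.929, power 0.82.
- Exact binomial: reject at 35 or fewer, or 55 or more, of 90 (two-sided size 0.045), power 0.812.

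The stated 0.80 reproduces as a one-sample test. The subgroup figures do so roughly: n = 45 at 0.71 gives 0.79 (exact) to 0.83 (normal); n = 30 at 0.74 gives 0.77 (exact) to 0.78 (normal).

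**2. The two-subgroup figures.** These are 95% half-widths, 1.96 × √(2p(1 − p)/n).
- p = 0.5: 0.253 at n = 30, 0.219 at n = 40, 0.207 at n = 45. The plan gives 0.25 at 30 and less than 0.20 at 40; the latter is not met at p = 0.5.
- p = 0.9: 0.152 at n = 30 and 0.124 at n = 45, against the stated 0.15 and 0.12.

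They describe the precision of a difference in proportions. They are not a test and carry no power.

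**3. What the pooled test does when the apps are equivalent.** Suppose 65% improve in both arms. The n = 90 test against 0.5 still rejects with probability 0.812. A two-sample z test with 45 per arm rejects with probability 0.053 (exact), as it should. Rejection of 0.5 therefore carries no information on which app is better.

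**4. What the design can detect between arms (80% power, two-sided 0.05).**
- Continuous outcome, unadjusted: d = (1.96 + 0.84) × √(2/n) = 0.59 SD at 45 per arm, and 0.51 SD at 60 per arm if no one is lost.
- Binary, 0.65 v 0.50, 45 per arm: z = (0.15 × √45 − 1.96 × √(2 × 0.575 × 0.425)) / √(0.65 × 0.35 + 0.25) = (1.006 − 1.370) / 0.691 = −0.527, power 0.30. At 60 per arm it is 0.38.
- Binary, difference detectable at 45 per arm: 0.50 v 0.78. For comparator proportions from 0.30 to 0.65 the difference needed is about 0.24 to 0.29.

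**5. Hypotheses against planned analyses.**
- Time remitted or syndromal (a): no test or model is given.
- LFQ scores and subscales (a, e): no test or model is given.
- Decreased item scores (g): proportions are to be analysed, but no arm contrast is given.
- The logistic regression is optional, treats improvement as yes or no at end of study, and does not name arm.

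**The case against.** The best defence has three parts. The declared primary aims are adherence and attrition, and the plan never says that the 0.80 is power for a, e or g. The plan does foresee comparing two groups with a confidence interval, and 45 is half of 90. And in a trial of two randomized tools, arm is the obvious predictor of interest in the logistic regression; the talk of moderating factors and a final model hints at a treatment term.

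The part on primary aims stands as a limit on the point. A reader might infer that the sponsor claims 80% power for the comparison, or that the power calculation is wrong. The documents support neither: the calculation is right for the test it describes, and no passage attaches it to a, e or g. Even so, a stated hypothesis needs a stated analysis whatever its rank.

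The other two parts stand only in part. An interval for a difference would be a legitimate analysis, but the subgroups are not identified as arms and the figures concern proportions of subjects, not time in state or LFQ scores. The regression could carry arm, but it is optional, leaves arm unnamed, and deals only with a binary end-of-study result. If the n = 45 one-sample statement is read as one arm, that arm is still compared with 0.5, not with the other app.

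A reader might also infer that 0.5 is the wrong null because stable subjects stay in the denominator. The sentence can equally be read as treating stability as the null case, with rises and falls equally likely. Nothing says that stable subjects count as not improved, so I do not press this.

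**Conclusion.** The point holds and should be fixed before analysis. The three superiority hypotheses have no named between-arm analysis, and the stated power belongs to a pooled within-subject test that rejects about 81% of the time when both arms improve alike at 65%. This is more than missing detail, because the test that is specified cannot answer those hypotheses.

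The between-arm sizes (about 0.59 SD, or 0.50 v 0.78, at 45 per arm) rest on assumed 1:1 allocation and an unadjusted two-group comparison. Baseline adjustment could improve them; app switching, with subjects kept in their randomized arm, could dilute the difference. The 0.51 SD at 60 per arm applies only if no one is lost, whereas the plan itself allows for 30 losses. The conclusion that the test against 0.5 cannot separate the arms does not depend on these assumptions.

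**What to change.** 1. **Compare arms as randomized for a, e and g.** Keep subjects who switch app (allowed under Software) in the arm to which they were randomized.
   - Hypothesis a, clinical state: compare the proportion of post-baseline BISS visits (weeks 8, 16, 24, 32, 40, 52) in remitted status, and likewise in syndromal status. Each subject's fraction of visits or a repeated-measures model would serve. Adjust for week-0 BISS, site, and device if it is used to stratify, whatever their p-values. Fix the state cut-offs before analysis. Report the between-arm difference with a 95% interval.
   - Because early termination depends partly on BISS severity, add a sensitivity analysis that scores visits lost to it as not remitted (as syndromal for the syndromal outcome).
   - LFQ total and subscales (a and e): a between-arm comparison adjusted for the week-0 value.
   - Hypothesis g: the between-arm difference in the proportion of decreased scores on corresponding items, with an interval that allows for clustering by subject.
2. **Restate the power section.** Say that the 0.80 applies only to the within-subject test against 0.5, and label that test descriptive. Give the between-arm detectable differences from step 4 of the working with their assumptions. Correct the bound at n = 40, or state the proportion for which it holds.

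**Cost.** No new data: Table 1 already schedules the BISS-42 at seven visits and the LFQ at four. BISS cut-offs for the clinical states must be written, since the documents give none. State at visits only approximates the aggregate time in state that the trial sets out to assess. The stated detectable effect becomes less favourable.

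### The two-subgroup precision stated for size 40 (below 0.20) is about 0.22 at a proportion of 0.5, and both two-group sentences bound the difference rather than its margin of error

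*Combined protocol and SAP*

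**What the plan says.** All the precision statements are in the Plan of analysis paragraph of the combined protocol and SAP, under the heading Assess KIOS-Bipolar or eMoods.

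- **One sample, n=90:** "we will be able to estimate any proportion within 0.10 with 95% confidence". For proportions above 0.9 the stated precision is 0.06. Both figures are worded as distance from the true value.
- **Two subgroups, general case:** the limits are given as "less than 0.25 for subgroups of n=30 and smaller than 0.20 for subgroups of size 40". They are placed on the difference itself, at 95% confidence, and no proportion is given.
- **Two subgroups, high proportions:** the condition is worded "If the proportions are larger than 0.9 (i.e. less variable"). The limits for this case are again placed on the difference, in the form "the difference in proportions of two subgroups with n=30(45) is less than 0.15 (0.12").
- **Subgroup sizes elsewhere in the paragraph:** 30 and 45, for example "For subgroups of patients with n=45 we can detect 0.71 different from 0.5". Size 40 appears only in the general two-subgroup sentence.

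**The concern.** The general two-subgroup sentence pairs 0.25 at n=30 with 0.20 at n=40. Going from 30 to 40 per subgroup narrows a margin by a factor of sqrt(30/40) = 0.866, whereas 0.20/0.25 is 0.80. That is a reason to recompute the pair, though not in itself proof of an error, because the text gives both values as upper limits.

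The wording is a second matter. A sample size limits the error in estimating a difference. It cannot limit the difference itself, yet both two-group sentences are written as if it did.

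What is at stake is how precise a reader believes a comparison of two subgroups of 40 will be. Section C (Hypotheses) also expects persistence, on-time completion and satisfaction not to differ between groups, so a sentence that seems to guarantee a small difference could be misread as support for that.

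**Working it through.** **Inputs**

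- Confidence 95%, from the sentences themselves. Two-sided, z = 1.96, in line with the paragraph's tests at "0.80 power at two tail significance of 0.05".
- Subgroup sizes 30, 40 and 45, and one-sample size 90, from the same paragraph.
- Proportion p: 0.9 where the plan refers to proportions above 0.9. For the general two-subgroup sentence p is not stated. I assume 0.5 in both subgroups, the widest case, and examine other values below.
- Two independent subgroups of equal size n.

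**Formulas (normal approximation)**

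- One sample: 1.96 × sqrt(p(1−p)/n)
- Two subgroups: 1.96 × sqrt(2p(1−p)/n)

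**Step 1. Reproduce the plan's figures**

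| Case | p | Calculation | Result | Stated |
|---|---|---|---|---|
| One sample, n=90 | 0.5 | 1.96 × sqrt(0.25/90) | 0.103 | 0.10 |
| One sample, n=90 | 0.9 | 1.96 × sqrt(0.09/90) | 0.062 | 0.06 |
| Two subgroups, n=30 | 0.5 | 1.96 × sqrt(0.50/30) | 0.253 | 0.25 |
| Two subgroups, n=30 | 0.9 | 1.96 × sqrt(0.18/30) | 0.152 | 0.15 |
| Two subgroups, n=45 | 0.9 | 1.96 × sqrt(0.18/45) | 0.124 | 0.12 |
| Two subgroups, n=40 | 0.5 | 1.96 × sqrt(0.50/40) | **0.219** | **0.20** |

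Five of the six round to the stated value. The sixth rounds to 0.22.

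**Step 2. Other interval methods at n=40, p=0.5**

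- Agresti-Caffo: 1.96 × sqrt(0.50/42) = 0.214
- Newcombe (from Wilson limits): 0.209

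Neither is below 0.20.

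**Step 3. Size of the gap**

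- Ratio: 0.2191/0.20 = 1.095, so the margin is about 10% wider than stated.
- Confidence carried by a 0.20 margin at n=40: 2Φ(0.20/sqrt(0.5/40)) − 1 = 0.926.
- Size needed for 0.20: 1.96² × 0.5/0.20² = 48.02, so 49 per subgroup.

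**Step 4. Where the stated bounds do hold (normal formula)**

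| Proportions | n=30 | n=40 |
|---|---|---|
| 0.5 and 0.5 | 0.253 | 0.219 |
| 0.704 (or 0.296) in both | 0.231 | 0.200 |
| 0.75 in both | 0.219 | 0.190 |
| 0.5 and 0.8 | 0.229 | 0.198 |

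With unequal proportions the formula is 1.96 × sqrt((p1(1−p1) + p2(1−p2))/n). For 0.5 and 0.8 at n=40 this is 1.96 × sqrt(0.41/40) = 0.198.

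**Step 5. If 45 was meant (p=0.5)**

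- Normal: 1.96 × sqrt(0.50/45) = 0.207
- Agresti-Caffo: 1.96 × sqrt(0.50/47) = 0.202
- Newcombe: 0.198

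**The case against.** **The figures are upper limits and no proportion is stated.** This is the strongest objection, and part of it stands. A reader might infer that the mismatch holds whatever the proportion, because scaling 0.25 from n=30 to n=40 gives 0.25 × sqrt(30/40) = 0.217. The documents do not support that. The scaling treats a limit of 0.25 as an exact value. At a shared proportion of 0.75, or at 0.5 against 0.8, both limits are true. The error therefore rests on taking p near 0.5 in both subgroups. That reading is inferred, but the paragraph points to it: 0.5 gives the 0.25 at n=30, the n=90 sentence covers any proportion, and proportions above 0.9 are set apart as the less variable case. Nothing restricts the general sentence to proportions away from 0.5.

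**The paragraph rounds loosely.** Read strictly, the other five figures also slightly exceed their stated limits. That is true, but each rounds to the printed value at two decimals, and 0.219 does not round to 0.20.

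**A one-sided 95% limit would satisfy both bounds** (0.212 at n=30, 0.184 at n=40). It does not fit the rest of the paragraph: at n=90 it gives 1.645 × sqrt(0.25/90) = 0.087, not 0.10.

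**Size 40 is probably a slip for 45.** This is plausible. The sentences on either side use 45, which is half of the 90 expected completers, while 40 matches neither that nor a site target in section B (50, 35 and 35). The documents do not settle it. At 45 the normal margin is 0.207, only 0.007 above the stated value. Newcombe meets the limit at 45 (0.198), but it gives 0.238 at n=30, so it is not evidently the method behind the 0.25.

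**The wording on differences is harmless.** Largely accepted. A reader might infer that the plan promises small true differences, but the one-sample sentences just before show that a margin was meant. This is a correction of wording, not of reasoning.

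**Conclusion.** The point holds and is minor. If the general sentence covers proportions near 0.5, subgroups of 40 give a 95% margin of about 0.22, and the stated 0.20 is too optimistic by about 0.02. This assumes two independent subgroups of equal size, two-sided 95% confidence and p=0.5 in both. If 45 was intended, the excess nearly disappears and its sign depends on the interval method, so the 10% figure applies only to size 40.

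The wording defect in the two-group sentences does not depend on any of these assumptions. The 0.15 and 0.12 for high proportions reproduce at 0.9 and need no numerical change.

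A reader might go further and infer that the trial is too small. The documents do not support that: the 0.20 is not linked to the enrolment of 120, to an equivalence margin, to a decision rule or to any named comparison.

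**What to change.** 1. Confirm from the sponsor's calculation whether the subgroup size is 40 or 45.
2. State the margin as about 0.22 for n=40, or about 0.21 for n=45 (normal formula).
3. Add the assumed proportion (0.5 in both subgroups) and the formula.
4. In both two-group sentences, describe each figure as the 95% margin of error of the estimated difference in proportions, in line with the one-sample sentences.

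The cost is an edit to two sentences: one figure and possibly one subgroup size, a short statement of the assumption and formula, and one phrase used twice. Enrolment, endpoints and analyses do not change.
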